PROTOCOL TITLE: The effect of a collaborative art therapy and physical therapy intervention on children undergoing a hematopoietic cell transplant: a randomized clinical trial

PRINCIPAL INVESTIGATOR: [name], PT, PhD, PCS

Objectives / Specific Aims

Aim 1: In children undergoing HCT during in-patient care, does a randomized group receiving a combination of PT plus AT have improved functional activity level outcomes of selfcare and mobility as measured by the Pediatric Evaluation of Disability Inventory Computerized Adaptive Test (PEDI CAT) and the 6-Minute Walk Test (6MWT), compared with a group receiving PT only.

Hypothesis 1: Children receiving the combined intervention of PT plus AT will demonstrate greater improvements in selfcare and mobility skills.

Aim 2: Do children receiving PT plus AT have different physiological (sympathetic or parasympathetic) and emotional responses to oil pastels and gouache as measured by respiratory sinus arrhythmia (RSA) derived from heart rate variability (HRV) and Self-Assessment Manikin (SAM) scores during each of the daily AT sessions.

Hypothesis 2: Oil pastels or gouache AT will generate a greater RSA value in the direction of needed parasympathetic activity and balance in the emotions of valence, arousal, and dominance.

Aim 3: In children receiving PT plus AT, determine if there is a stronger association between the RSA values of oil pastels or gouache AT and an increased walking distance as measured by accelerometry during daily PT sessions.

Hypothesis 3: The media that best generates a parasympathetic RSA value and emotional balance will be associated with a greater walking distance.

2.0 Background

Overview: For the 13,000 children with hematological disease undergoing allogeneic hematopoietic cell transplant (HCT) in the United States¹, art therapy (AT) and physical therapy (PT) are prescribed at a rate of approximately 50%² to minimize negative treatment consequences. Anxiety, pain, loss of control as well as reductions in physical conditioning, functional mobility, selfcare, and motor skills are common consequences associated with HCT in children and will inform this proposed research project's outcomes and aims.³

As we consider the impact of AT and PT on children undergoing HCT, the AT literature generally emphasizes AT's effect on emotional health (e.g., pain, anxiety) and PT's on physical health (e.g., mobility, selfcare). The Model of Art Therapy in Management of Pediatric Chronic Pain^{4,5} fosters improvements in anxiety and pain following AT that then promote greater compliance with medical treatments.^{4,5} (Appendix 1). It is this theoretical premise that supports our proposed project's suggestion that a collaborative treatment of AT and PT would be more effective than only providing AT or PT or providing both independent of each other. We believe the interconnected use of AT to reduce emotional distress prior to PT would not only enhance PT compliance, but also provide greater opportunity for improvements in physical performance and overall health.

Art Therapy Evidence in Pediatric HCT

The American Art Therapy Association (AATA) defines AT as an integrative mental health and human services profession that enriches the lives of individuals, families, and communities through active art-

making, creative process, applied psychological theory, and human experience within a psychotherapeutic relationship.⁶ This AT process involves three important components: 1) patient, 2) art therapist, and 3) art making materials that interact collectively to impact emotional and health outcomes. In a 2019 review entitled Effectiveness of Art Therapy with Pediatric Populations Affected by Medical Health Conditions: A Systematic Review, Clapp acknowledges that the goals of AT interventions focused on enhancing emotional understanding and promoting symptom management.⁵ Similarly, yet specific to pediatric oncologic health conditions, the efficacy for AT is drawn from descriptive qualitative studies that support: 1) emotional communication in response to anxiety, fear of death, loss of control, 2) a strategy by which to distract and/or cope, and 3) symptoms, anxiety, and pain amelioration.^{7,8} It is clearly stated in this systematic review that the majority of AT research findings are based on qualitative methods and, although this qualitative work is informative and guiding, the need to objectively quantify the effectiveness of AT and its impact on health outcomes has been noted and acknowledged within the literature.⁹ In fact, direct calls for more robust studies to examine AT's impact on health outcomes have been documented^{5,10} and are necessary, not only to increase the uptake of AT in children undergoing HCT, but other pediatric populations as well.

Physical Therapy in Pediatric HCT

The American Physical Therapy Association defines physical therapy as the promotion, maintenance, and restoration of health through physical examination, diagnosis, prognosis, patient education, physical intervention, rehabilitation, disease prevention and health promotion.¹¹ Physical therapists are considered movement experts¹¹ and address illnesses or injuries that interfere with individuals' ability to move and perform functional activities in their daily lives such as mobility and selfcare. The efficacy of physical therapy interventions using a variety of therapeutic exercise in pediatric populations has been well demonstrated in children with juvenile idiopathic arthritis¹², having chronic pain¹³, and with hemiparetic cerebral palsy.^{14,15} Although efficacy is not yet supported, the implementation of exercise programming by physical therapists in the area of pediatric HCT is becoming more common to mitigate deconditioning and functional losses during the treatment course.^{16,17} For the children who receive PT, evidence indicates that exercise interventions across the continuum of HCT improve functional mobility, abilities of daily living, strength and endurance¹⁷, and promotes a reintegration into everyday participation. Yet in spite of these positive gains, prolonged motor delays following HCT remain common.¹⁸⁻²⁵

While a few PT studies have incorporated the use of emotional wellbeing education into exercise interventions to improve strength and endurance in patients during HCT^{17,26}, in the reality of clinical settings where HCT take place, the primary focus of PT is therapeutic exercise and activities geared toward physical health. Knowing that emotional health is as important as physical health and with evidence of AT's positive impact on emotional health for children undergoing HCT, it seems logical that collaborative interventions incorporating AT and PT would boost health outcomes. As such, we broadly hypothesize that children undergoing HCT in an in-patient setting receiving AT immediately prior to PT will display greater improvement in the body function (i.e., physiologic and emotional) and activity level (i.e., mobility and selfcare) outcomes across the International Classification of Functioning, Disability and Health²⁷ (Appendix 2) than children only receiving PT. By exploring this broad hypothesis, we create an excellent opportunity to also investigate in greater depth the impact of AT media on body function and activity level outcomes.

Motivation 1: Innovative use of quantifiable RSA/HRV to examine the impact of art therapy on the Autonomic Nervous System (ANS) in children undergoing HCT.

Our first motivation for this research is believing that AT can physiologically improve the state of the ANS which can lead to better health outcomes for children with health conditions and disability and specific to this proposed study- children undergoing HCT. The Children's Hospital at MUSC has an active in-patient HCT program and for that reason, we have an opportunity and are proposing that the use

a collaborative treatment of AT and PT, as compared to PT only, will improve mobility and selfcare outcomes in children undergoing HCT. Because of emotional impairments (i.e., pain and anxiety) that are associated with hematopoietic disease and HCT in children²⁸, the ANS demonstrates a dominance toward fight or flight or unstable homeostasis.^{29,30}

To better understand this ANS dysfunction, a basic review is provided. The ANS consists of two systems: sympathetic (SNS) and parasympathetic nervous systems (PNS) that shape vagal tone by exerting influence upon the vagus nerve. The SNS creates a fight or flight state while the PNS fosters a rest and digest condition. Homeostasis is created when the two systems work in unison to create balanced vagal tone upon the vagus nerve. Intrinsic (e.g., hydration, body temperature) and extrinsic factors (e.g., bone marrow biopsy, chemotherapy treatment) can facilitate or interrupt this homeostasis. It is important to recognize that although the SNS and PNS are interconnected, the SNS provides dominant and steady stimulation to the vagus nerve while the PNS providing ongoing, yet variable, braking to the SNS. It is this relationship that promotes either homeostatic stability or instability as intrinsic and extrinsic factors demand.

Porges' Polyvagal theory³¹ provides a more in depth understanding of the relationship between vagal tone and ANS. He proposes that 3 phylogenetic stages exist within the human ANS that are ordered to allow for 1) social communication, 2) mobilization or fight-flight, and 3) dissociation or immobilization. (Appendix 3.) Activation of the myelinated ventral vagus, in which the SNS and PNS are providing stimulation and braking to the vagus nerve, allows for homeostasis and social communication. This is the desired and more healthy state for human beings including children undergoing HCT. When intrinsic or extrinsic factors trigger the SNS with vagal braking inhibited, sympathetic dominance or a fight-flight responses manifest. Because of medical interventions (extrinsic) as well as anxiety and pain (intrinsic), this is this stage in which most children having HCT dwell.^{29,30}

Respiratory sinus arrhythmia is a direct measure of this vagal tone³¹ and is derived from HRV across the respiratory cycle. Heart rate variability is defined as the variation between consecutive heartbeats³³ or beat to beat variability³². It is considered a validated physiological mechanism for evaluating the state of the ANS and more specifically emotional responsivity. In a systematic review, Kirizawa and colleagues²⁹ have advocated for the use of HRV as a physiological marker to evaluate ANS function in individuals with leukemia. The heart's ability to demonstrate high variability is considered advantageous, but often undesirable intrinsic and extrinsic factors decrease variability. One such factor is the treatment of HCT in children with hematopoietic disease. Because RSA/vagal tone/HRV has been successfully used to investigate the ANS in pediatric traumatic brain injury³⁴, premature babies³⁵, and children with autism spectrum disorders^{36,37}, we believe its use with children undergoing HCT in our study is promising. An additional advantage is the fact that the collection of RSA/HRV is non-invasive and improved technological development has led to the delivery of reliable, portable HRV monitors. Again, making its use appealing with children undergoing HCT.

Motivation 2: Exploring the effect AT media on RSA/HRV, emotional state, and the health outcome of mobility in children undergoing HCT.

Recognizing that AT and certain aspects of AT media have promoted changes in the ANS as measured by HRV in children and adults³, and that calls have been made for the use of HRV in studies exploring AT interventions^{5,9,10}, we arrive at our second research motivation: to capture RSA/HRV during AT interventions in order determine if one type of media leads to improved changes in the ANS as captured by HRV/RSA, emotional ratings, and daily mobility.

Understanding the relationship between patient, therapist, and the art making material is critical to generate effective patient outcomes. Much of the AT evidence discusses the important bond developed

between patient and therapist; however, awareness considering the qualities of the art making material has had limited examination. Despite the known interactive role of media through kinesthetic, tactile, perceptual, and symbolic input, media make play a more important than has previously been suggested. Kramer cleverly has described the media as the third hand, which contributes to an art therapist's ability to steer the creative and restorative process.^{38,39} The Expressive Therapies Continuum (ETC) provides a conceptual model with developmental hierarchical levels that guide the assessment and application of art making materials during art therapy. (Appendix 4). It consisted of four levels:

- 1) kinesthetic/sensory: sensory motor experience gained through the body's interaction with the material
- 2) perceptual/affective: emotional connection established by interaction with materials and creation of form/product
- 3) cognitive/symbolic: emergence of symbolic or abstract thought centered about the product/form allowing for sophisticated, formative thought
- 4) creative: communication or expressive interaction between the individual and the product/form promoting personal well-being whether by providing closure to a false sense of self or elation to restoration of an authentic sense of self.⁴⁰⁻⁴³

These levels often interactive or overlap, but advancing through each of these levels over one art therapy session may not be achieved. This is especially the true for creative, the highest level.⁴³

Art therapy literature provides some degree of prescription for the use of specific media. Across an ordinal scale and based on fluidity, rankings for media from least to most emotionally engaging are pencils, oil pastels, and gouache.³⁹ The use of markers and pencils is said to offer structure, control, and a limited emotional response that does not generate anxiety. Oil pastels or chalk are noted to afford moderate fluidity and tactical enrichment through touching and smearing, thereby resulting in greater emotional arousal (moderate anxiety) than pencils.^{42,44} When not using a brush, the fluidity offered by gouache painting yields high levels of emotional engagement and anxiety; however, use of a brush decreases emotional engagement. It is important to consider that gouache painting has also being described as liberating.^{45,46}

As has been encouraged by AT literature and organizations, several studies have examined the impact of media. The first study looked at media's impact on the outcome of emotional responses and the second on HRV. Pesso-Aviv and colleagues explored the effects of pencils, oil chalks, and gouache paint on anxiety and self-control using survey data on 41 males between the ages of 7 to 9 years, who although not reported within the narrative appear to have been healthy, typically developing youth. Ten intervention session were provided for each of the three different media groups. Surprisingly, the results indicated no change in anxiety and self-control outcomes. This may be possibly explained by the youth being healthy and typically developing with little to no impairments in anxiety and self-control, thus, creating a ceiling effect with little space for documenting improvement. For children undergoing HCT, we know that emotional engagement and anxiety are problematic so media's impact may be more detectable in this group. In the second study, Haiblum-Itskovitch and researchers hypothesized that emotional and ANS responses as measured by RSA/HRV values would be more reflective of PNS activity as fluidity of the media decreases in a normative sample of adult participants; thus, pencils would offer the greatest PNS activity followed by oil pastel and then gouache with brush. Surprisingly, results indicated that oil pastels resulted in the greater PNS activation than gouache while also corresponded to more meaningful emotional engagement. Thirty-five percent of the variance in the PNS value was explained by the media with a change in the RSA value of 1 representing the effect size needed for detecting a meaningful difference between materials. The author offered the possibility that the oil pastels facilitated greater tactile input which like fluidity may also played a role in ANS activity and emotional engagement. Based on the above information and considering that no study has explored the use of RSA/HRV as a physiological measure by which to evaluate a media's impact on a population of children with a health

condition, our proposed study seeks to accomplish this by evaluating 2 media's impact on physiological (RSA/HRV), emotional (SAM), and health outcomes (mobility) of in children undergoing HCT.

3.0 Intervention to be studied (if applicable)

Side-by-side integration of AT and PT has not been examined and we propose to conduct a clinical trial in which for two weeks daily (Monday-Friday), 20 children between the ages of 3-18 years will be randomly assigned into one of two groups: 1) collaborative intervention: 45 minutes of AT immediately followed by 30 minutes of PT or 2) PT only intervention: 30 minutes. During the collaborative intervention of week 1, oil pastels will be the media and week 2 gouache painting without brush.

Treatment: 45 minutes of AT closely followed by 30 minutes of PT OR 30 minutes of PT.

AT treatments will seek to reduce sympathetic dominance/physiological and emotional distress. Oil pastels will be used for Days 1-5 and gouache painting for days 6-10. Art therapy is a collaborative, interactive, and iterative process that evolves across the session between the child and art therapist, as such, outside of the actual change in medium, there is no study specific art therapy prescription or protocol. Art therapy sessions will occur in the child's room.

PT treatments will seek to prevent physical deconditioning and encourage mobility, ambulation, and selfcare participation based on participant's ability. Physical therapy sessions will occur in the child's room and on the HCT unit.

The same art and physical therapist and art therapist will conduct children's session across the 2-week study duration. This art and physical therapist commonly work on the HCT unit. The coordinator again will monitor all sessions to ensure the following of study procedures.

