5.0 Inclusion and Exclusion Criteria/ Study Population

Inclusion criteria: Children between the ages of 4 and 18 years undergoing HCT in response to hematological disease during the in-patient hospital treatment phase.

Exclusion criteria: Children with central nervous system impairments (e.g., cerebral palsy), other genetic diseases (e.g., Down syndrome), and cognitive impairment will be excluded from study participation.

Children undergoing HCT were chosen as this study's population because they often receive intermittent and stand-alone AT or PT. We believe more daily PT and/or AT as well as the collaboration between PT and AT will improve health outcomes. Because children display continual cognitive, behavior, and motor development changes, this study chose not to involve adults undergoing HCT. The outcomes for children and adults undergoing HCT cannot be validly compared. This study has no exclusions for any specific sex/gender or racial/ethnic group.

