10.0 Study Design / Methods

Design: Randomized clinical trial to compare collaborative AT and PT to only PT in children undergoing HCT.

Using excel, the study coordinator will randomize each participant to either the PT and AT or PT only group. Each group will be assigned 10 participants.

Power

With a recruitment expectation of 30 participants, we expect a 30% drop out rate leaving 20 enrolled participants and feel confident that this study's aim 2 and 3 will be successfully powered to identify statistical significance ($p<0.05$) in outcomes. For Aims 2 and 3 which involve the collection of clustered data for HRV, SAM, and walking distance, in order to identify a medium effect, 80% or 90% power will be achieved with 61 or 82 measurement points respectively.^{54,55,66,67} Accounting for a dropout rate of 30%, the expected number of participants is 20. With 10 participants in the intervention group, 100 measurement points for HRV, SAM, and walking distance each are expected; thus, ensuring adequate power for aim 2 and 3.

For the PEDI CAT and 6MWT, to achieve 80% power, the projected sample size in each group is estimated to be 16 and 20; therefore, we proposed that we may not be adequately powered for aim 1.^{51,68} However, findings attributed to aim 1 will provide pilot data to inform a larger randomized control trial. Although aim 1 may not be adequately powered, the published minimal detectable change (MDC) for the PEDI CAT selfcare and mobility domains are 2.2 and 2.5 respectively while the Minimally Clinically Important Difference (MCID) for the 6MWT is 7%.^{69,70} Although, power to find a statistically significant difference may be inadequate, we expect to observe this level/magnitude of improvement in our proposed study. Variation values from this aim will provide data that are essential to guide future research.

Data Analyses

Aim 1: In children undergoing HCT during in-patient care, do a randomized group receiving a combination of Physical Therapy (PT) plus Art Therapy (AT) have improved functional activity level outcomes of self care and mobility as measured by the Pediatric Evaluation of Disability Inventory Computerized Adaptive Test and the 6-Minute Walk Test, compared with a group receiving PT only.

Hypothesis 1: Children receiving the combined intervention of PT plus AT will demonstrate greater improvements in self care and mobility skills.

Statistical Test: Independent sample t-tests

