Aim 2: Do children receiving PT plus AT have physiological (sympathetic or parasympathetic) and emotional responses to oil pastels and gouache as measured by respiratory sinus arrhythmia derived from heart rate variability and Self-Assessment Manikin scores during each of the daily AT sessions.

Hypothesis 2: Oil pastels or gouache AT will generate a RSA value in the direction of needed parasympathetic activity and balance the emotions of valence, arousal, and dominance.

Statistical Test: Repeated measures generalized linear regression

Aim 3: In children receiving PT plus AT, determine if there is a stronger association between the RSA values of oil pastels or gouache AT and an increased walking distance as measured by accelerometry during daily PT sessions.

Hypothesis 3: The media that best generates a parasympathetic RSA value and emotional balance will be associated with a greater walking distance.

Statistical Test: Repeated measures generalized linear regression

Data Collection

The 10-day intervention will begin on approximately Day 15 of HCT. Pre-test (Pediatric Evaluation of Disability Inventory and 6-Minute Walk Test) will be collected on Day 14. The same post-test data will be collected the day following the tenth day of intervention.

During the 10 days of intervention, the Self Assessment Manikin, heart rate variability, and walking distance will be collected daily.

The study coordinator will be responsible for storing all data. All documentation and data concerning each participant will be coded to protect confidentiality. All data collection and storage processes and locations will use study equipment (i.e., heart rate variability monitors, computers, College of Health Professions DA server) that is password protected, encrypted, and behind the MUSC firewall. All study related equipment will be locked in the office of the PI when not in use. There will be no transfer of data to a third party.

Procedures

- 1) IRB approval
- 2) Begin participant enrollment
- 3) Collaborate with HCT team to initiate recruitment and share study flyer
- 4) PI will obtain informed consent from participants in the hospital or electronically through MUSC secure email.
- 5) Randomize participant to AT and PT or PT only
- 6) Approximately Day 14 of HCT complete pre-test (Pediatric Evaluation of Disabilities Inventory and 6-Minute Walk Test)

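### Aim 1 randomises 20 children across a 14–15 year age span with no age stratum and no age term, which costs precision and interpretability but does not bias the test

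*Combined protocol and SAP*

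**What the plan says.** - **Age range.** Section 3.0 says "20 children between the ages of 3-18 years will be randomly assigned into one of two groups". Section 5.0 admits "Children between the ages of 4 and 18 years undergoing HCT". The span is 15 years in one place and 14 in the other.
- **Allocation.** Section 10.0: "Using excel, the study coordinator will randomize each participant to either the PT and AT or PT only group", and "Each group will be assigned 10 participants". No stratum, block or minimisation factor is named.
- **Aim 1 analysis.** Section 10.0: "Statistical Test: Independent sample t-tests". No covariate is listed. The hypothesis is that "Children receiving the combined intervention of PT plus AT will demonstrate greater improvements in self care and mobility skills", but the plan does not say whether the change or the post-test value is tested.
- **Aim 1 outcomes.** Section 4.0 names the 6MWT and the PEDI-CAT self-care and mobility domains. The PEDI-CAT is to be scored in both a criterion-referenced (scaled) and a norm-referenced form.
- **Age and development.** Section 5.0 justifies leaving out adults with the words "Because children display continual cognitive, behavior, and motor development changes".
- **Power.** Section 10.0 projects 16 (PEDI-CAT) and 20 (6MWT) per group for 80% power, concedes that Aim 1 may be underpowered at 10 per group, and treats it as pilot data.
- **Aims 2 and 3.** These use only the PT plus AT arm. Section 10.0 gives "Statistical Test: Repeated measures generalized linear regression" and lists no model terms.

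**The concern.** The plan regards development during childhood as important enough to rule out comparison with adults, yet it ignores age across almost the whole of childhood. A preschool child and an 18-year-old can be expected to differ in walking distance and in a criterion-referenced function score whatever therapy they receive. With 10 children per arm, chance can easily leave one arm visibly older.

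Two things are at stake. The first is precision in the aim that the plan already calls underpowered. The second is interpretation: a difference between arms that also differ by two or three years in mean age will be questioned, and the variance estimates meant to guide the next trial will contain age spread that a later design could remove.

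**Working it through.** **1. The plan's own figures.** No effect size or SD accompanies the 16 and 20 per group, so they cannot be reproduced forwards. Solving backwards (two-sample t, two-sided 5% assumed, 80% power) gives standardised differences of d = 1.02 for n = 16 and d = 0.91 for n = 20. At 10 per arm these have power of 58% and 49%, consistent with the plan's admission.

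**2. Chance age imbalance.** Assumption: ages uniform over the stated range, so SD = span/√12, which is 15/√12 = 4.33 years (3–18) or 14/√12 = 4.04 years (4–18). The SD of the difference in mean age is SD × √(1/10 + 1/10), which is 1.94 or 1.81 years. From 200,000 simulated allocations:

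| Allocation | Range | SD of difference | 2 years or more | 3 years or more |
|---|---|---|---|---|
| As planned | 3–18 | 1.94 | 30% | 12% |
| As planned | 4–18 | 1.81 | 27% | 10% |
| Two bands, each split 5/5 | 3–18 | 1.04 | 5% | 0.3% |
| Two bands, each split 5/5 | 4–18 | 0.97 | 4% | 0.1% |

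**3. What a 2-year gap does to one result.** If age explains a share R² of the variance of the analysed score, the gap moves the arm difference by √R² × 2/4.33 SD. At R² = 0.30 this is 0.548 × 0.462 = 0.25 SD, about a quarter of the implied d. At R² = 0.05 it is 0.224 × 0.462 = 0.10 SD.

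**4. Gain in precision.** R² is not in the documents, so it is varied. The ratio of 95% interval widths, with age in the model against the plan's t-test, is approximately

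(t₁₇/t₁₈) × √[(1 − R²)(1 + v)], with t₁₇/t₁₈ = 2.110/2.101 = 1.0042.

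Here v is the price of estimating the age slope. Without strata v = 1/16 = 0.0625. With two bands it shrinks with the squared imbalance: (0.97/1.81)²/16 = 0.018. With bands and age together:

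| R² | Width ratio | Interval |
|---|---|---|
| 0 | 1.013 | about 1% wider |
| 0.05 | 0.988 | about 1% narrower |
| 0.10 | 0.961 | 4% narrower |
| 0.20 | 0.906 | 9% narrower |
| 0.50 | 0.716 | 28% narrower |

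Simulating the same comparison agrees to within half a percentage point. Allowing for that approximation, the rounded range is 1–1.5% wider at 0, 1–2% narrower at 0.05, about 10% at 0.20 and about 29% at 0.50. The break-even R² is 1 − 1/1.013² = 0.03 with bands. Without them the ratio at R² = 0 is 1.035, so it is 1 − 1/1.035² = 0.07.

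**5. Power from adjustment alone (v = 1/16).** For R² = 0, 0.1, 0.2, 0.3 and 0.5, power moves from 58% to 55, 60, 65, 71 and 84% (d = 1.02), and from 49% to 46, 50, 55, 60 and 75% (d = 0.91).

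**6. Aims 2 and 3.** Each child in the combined arm receives both media. In a simulation with a true media contrast of 0.5 and an additive age effect, the estimate was 0.50, 0.50 and 0.49 when the arm's mean age was near 6, 10.5 and 15: age cancels within child. For Aim 3, with assumed age slopes and no within-child association, the pooled slope of distance on RSA was 24 units across the full age range and 5 in a narrow young arm, while the within-child slope was about 0 in both.

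**The case against.** - **Chance imbalance is not bias.** This stands. A randomised t-test keeps its error rate, and the cost is precision and readability only.
- **The gain may be negligible.** The hypothesis speaks of improvement, pre- and post-tests are taken, and the benchmarks are change thresholds (MDC and MCID). That points to change scores, for which age may explain little; the benefit at R² = 0.05 is then 1–2%. Adjusting for baseline would probably absorb much of the age effect as well. This stands as a limit on size, but the plan does not state which score is tested.
- **One outcome is already age-adjusted.** Correct: norm-referenced PEDI-CAT scores need no age term. The exposure lies in 6MWT distance and the scaled scores.
- **The banded figures are best case.** They assume bands of exactly 10 split 5/5. With band sizes left to chance (simulated over a 15-year span with block sizes 2, 4 and 10), a gap of 2 years or more occurs in 5–9% of trials and exact 10/10 in only 52–75%. The balance is still much better than the planned 30%.

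A reader might also infer that an age-lopsided arm skews Aims 2 and 3. The documents do not support that. Neither aim compares arms, and an additive age effect drops out of the within-child media contrast. The arm's age mix affects which ages the results describe, or the size of the media effect if age modifies it, for which the plan offers no evidence. Nor is the arm likely to be almost all young or all adolescent: with 10 younger and 10 older children, a split of 7:3 or worse has an 18% chance, but 8:2 or worse only 2.3%. Age may confound RSA and walking distance in Aim 3, but it would do so with perfectly balanced arms, and stratifying would not cure it.

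**Conclusion.** The point holds for Aim 1 as an optional improvement, not a flaw that invalidates the comparison. No age stratum is named, the t-tests are unadjusted, and a gap of 2 years or more in mean age would arise in roughly 27–30% of allocations if ages are spread evenly. The precision at stake runs from a loss of about 1–1.5% in interval width to a gain of about 29%, for an age R² between 0 and 0.5. That R² is an assumption; the upper end is plausible only if post-test values are analysed. A larger claim, that adjustment is worth several extra children per arm, would need an R² that the documents do not supply. Absence of an age term is established for Aim 1 only, because the Aims 2 and 3 model terms are not specified at all.

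**What to change.** 1. Reconcile the age range between sections 3.0 and 5.0.
2. State whether Aim 1 tests change or post-test values.
3. For 6MWT distance and scaled PEDI-CAT scores, replace the t-test with a linear model containing arm and age. Age band is an alternative, but two bands carry only about 75% of the variance of evenly spread ages. Leave norm-referenced PEDI-CAT scores without an age term.
4. Prepare the Excel list in two age bands, cut near the middle of the reconciled range and balanced 1:1 within each band. This must be done before the first child is randomised.

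The cost is a second column in the list and a sentence in the analysis section. The downsides are one degree of freedom, a final split that may not be exactly 10/10, and slightly more predictable allocation. Predictability matters here because the coordinator who randomises also handles the collection and scoring of Aim 1 outcomes, so block sizes should not be guessable.
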